4.2 Randomization and Blinding

A total of 44 randomized blocks are needed for the study. For random assignment and sequencing purposes, each randomized block consists of five integers that correspond to the four treatment and one control group assignment. The VA Pittsburgh Investigational Drug Service (IDS) Pharmacist will randomly determine which integer corresponds to the control group and the integers corresponding to the

four treatment groups; this random assignment will only be done once, and the same integers will correspond to the assigned groups across all blocks. The Investigational Drug Service Pharmacist will use a randomizer function available on www.random.org. In order to maintain the blind, the control and treatment group assignments will not be divulged to any study staff other than the anesthesia care team member who prepares the nerve block injections. The sequence of treatment/control assignments within each of the randomized blocks will be determined by the VA Pittsburgh StatCore using the sequence generator at website random.org. Each block will have a separate sequence generated for it.

The randomization scheme will be prepared before the start of the trial. Sequentially numbered and sealed envelopes containing the randomized control or treatment group assignment will be provided by the Investigational Drug Service (IDS) Pharmacist. The IDS Pharmacist will retain the sealed envelopes and will be responsible for providing them to the PI or designee as requested prior to the scheduled procedure. The PI or designee will then provide the sealed envelope to the nerve block drug mixer. The IDS Pharmacist will coordinate the provision of the nerve block drugs. The drugs will be stored in an automated dispensing cabinet and accessible only to the designated nerve block mixers.

After a subject has been enrolled, the study coordinator will submit a Treatment Allocation Request form to the IDS Pharmacist.

- 1) The Treatment Allocation Form will indicate the subject's criteria:
 - a) Age: ≤ 69 or > 69 years
 - b) Type of procedure: total knee replacement or total hip replacement
 - c) Diabetes status: present or absent
- 2) Based on the criteria noted on the Treatment Allocation Request form, the IDS Pharmacist will provide the next available treatment assignment envelope.

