5.0 Statistical Analysis

5.1 Analysis Plan

Data will first be assessed for outliers (+/- 2 SD from the mean) and normality. Outliers will be corrected, if possible, or dropped from the analyses. Distribution, measures of central tendency, variability, and normality will be examined. Data transformations or non-parametric techniques will be applied as needed. We will delete observations with missing values. Spearman correlation coefficients will be computed to examine associations between nerve block drug treatments, replacement surgery

type (hip versus knee), and the outcome measures (SF-MPQ, SF-8, SF- 36, WOMAC, FIM, repeated chair stand test, Opioid Symptom Distress Scale, Defense and Veterans Pain Rating Scale and its Supplemental Questions) from all time points (1 day, 2 day, 3 day, 4 day, Follow-Up Visit 1, Follow-Up Visit 2). Associations between the outcomes across time points will also be examined with Pearson (SF-MPQ, SF-8, SF-36, WOMAC, repeated chair stand test, Opioid Symptom Distress Scale) and Spearman (FIM, Defense and Veterans Pain Rating Scale and its Supplemental Questions) correlation coefficients. We will test all hypotheses and aims by conducting longitudinal multi-level modeling. The level-one unit will be the repeated measures across time, the level-two unit will be the individual patient, and the level-three unit will be nerve block type and surgical site (knee versus hip) groupings (with additional analyses involving age and diabetes status, reflecting the randomization strata). This mixed model procedure will allow the assessment of outcome and exposure variables relationships while adjusting for covariates, and separate assessments of fixed and random effects (i.e., group and individual-level data) using highly correlated repeated measures data. Covariates included in modeling will be age, diabetes status, gender, weight, smoking status, initial health status (e.g., baseline SF-8 / SF-36 and WOMAC), and concurrent general health status (e.g., daily SF-8, subsequent SF-36, and WOMAC).

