The **primary hypothesis** of an improvement in pain (measured by the SF-MPQ- version 2) 24 hr after surgery during in-hospital recovery comparing plain local anesthetics versus ISOC MMPNA will be tested using a mixed model. This procedure will test for nerve block drug treatment and surgical site (hip versus knee) effects, as well as an interaction between them. Differences in pain levels will also be examined across the study's day-of surgery, 1, 2, 3, and 4 day, and Follow-Up Visit 1 and Follow-Up Visit 2 time points. The secondary aims of short- and long-term physical therapy and rehabilitation-related benefits will also be examined for nerve block drug treatment and surgical site by a mixed model. The tertiary aim to determine differences in opioid-related side effects will use a mixed model. As with other analyses, there will be an examination for nerve block drug treatment and surgical site effects, as well as an interaction between them, along with analyses of the other randomization strata (age, diabetes) as described above.

The **exploratory aims** of physical therapy progress, return-to-home benefits, etc. will be examined using a mixed model. This procedure will test for nerve block type and surgical site effects, as well as an interaction between them. Number of days from the joint replacement procedure to the patient's home discharge will be assessed. Pain responses, as measured by the SF-MPQ – version 2, and use of postoperative opioids with additional measurement by the Opioid-Related Symptom Distress Scale will also be assessed. General health status will be evaluated with the SF-8 and SF-36. Measures of pain, analgesic side-effects, and general health status will be covariates included in the modeling of the effect of MMPNA on return-to-home.

Only after all data are analyzed and results are checked and verified by the biostatisticians will the study be unblinded.

5.2 Adverse Events. For adverse events, we will calculate cumulative probability using survival analysis techniques such as the product-limit estimator. Unlike proportions, product-limit estimators can be applied at various times following randomization, and can take into account when adverse events occur. The six-week incidence (and 95% CI) of individual adverse events by organ system and relatedness to the study will be calculated for each group. We will estimate the incidence of adverse

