The study drug is administered only once, at the time of the nerve block before surgery. So no adverse event would involve “continuous receipt of study drugs.”

We do not anticipate any withdrawn participants from the study, with the exception of those for which the anesthetic care plan was converted to GETA. This is because (i) the nerve blocks and/or spinal failed, or (ii) that the nerve blocks and/or spinal were appropriate for the “typical” surgical procedure. In further detail, the particular surgical procedure that was forced to a GETA anesthetic plan was likely atypically lengthy or complex, rendering the study case as likely not comparable to other enrolled/completed study participants. Therefore, we do not anticipate any further data collection as being representative of a scientifically meaningful “intent-to-treat.”

The basis of adverse event severity related to the study entails 1) association with the investigational drug or study treatment(s); 2) serious nature of the adverse event; and 3) unexpected nature of the adverse event. The nerve block drug involved in the active control group (bupivacaine) to which the experimental group drugs are added (clonidine-buprenorphine-dexamethasone) are not expected to create untoward surgical events and/or blood loss complications since none of these drugs alter physiologic coagulation. It is not anticipated that surgical complications that entail blood loss, of whatever severity, will be traceable to the nerve block treatment group. However, we will still record and grade estimated blood loss of the surgical procedure (<500 mL, 500-1L, > 1L) and determine any potential associations with nerve block treatment group.

Subjects withdrawn from study participation due to an adverse event will be replaced.

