APPENDIX 1: Study Calendar

	Screening Visit ^a	Baseline Visit	Day of surgery		Post-Op Day 1	Post-Op Day 2	Post-Op Day 3	Post-Op Day 4	Post-Op Day 5	Follow-Up Visit 1 ^d	Follow-Up Visit 2 ^{c, e}
			Pre-Procedure	Post-Procedure							
Clinical Assessments											
Informed Consent	X										
Determine Eligibility	X										
Demographics	X										
Orthopedic & IMPACT evaluation		X									
Crude Sensation in L2-L4 & L4-S3		X			X	X	X	X	X		X
Straight Leg Raise & Range of Motion		X			X	X	X	X	X		X
Functional Independent Measure (FIM)		X			X	X	X	X	X		X
Standing Balance Test		X			X	X	X	X	X		X
Single Leg Balance Test ^g		X									X
Gait Speed		X			X	X	X	X	X		X
Repeated Chair Stand Test		X				X	X	X	X		X
Stair Climbing Time		X									X
Physical Therapy/ Therapeutic Exercises					X	X	X	X	X		
Comorbidity (CIRS)		X									
Interim Changes											X
Discharge Disposition											X
Opioid Consumption					X ^g						
Anesthesia/Study Drugs			X								
Adverse Events		X	X	X	X	X					
Concomitant Medications		X	X	X	X	X					

	Screening Visit	Baseline Visit	Day of surgery		Post-Op Day 1	Post-Op Day 2	Post-Op Day 3	Post-Op Day 4	Post-Op Day 5	Follow-Up Visit 1	Follow-Up Visit 2 ^{c, e}
			Pre-Procedure	Post-procedure							
Questionnaires											
SFMPQ-2 ^b		X	X	X	X	X	X	X	X		X
DVPRS		X	X	X						X	X
DVPRS- in hospital ^b					X	X	X	X	X		
ORSDS ^b		X			X	X	X	X	X		
QOR-15 ^b		X			X	X	X	X	X		X
WOMAC		X									X
SF-8 ^b			X		X	X	X	X	X	X	
SF-36		X									X
Falls Questionnaire		X			X	X	X	X	X		X

a. The screening visit and baseline visit can be completed on the same day.

b. On post-op hospital days and post-op week 6 follow-up visits, these questionnaires will be completed before the subject has their first physical therapy session for the day.

c. If a patient decides to withdraw from the study after having their surgery, or is withdrawn by the study team during or after their surgery, they will be asked to complete Follow-Up Visit 2.

d. Follow-up visit 1 will occur with the patient's already scheduled standard of care follow-up orthopedic visits. Follow-Up Visit 1 may be performed as a phone call if necessary.

e. Follow up visit 2 will be scheduled to coincide with the patient's standard of care follow-up orthopedic visits.

f. Patient must pass the standing balance test first, before the single leg balance test can be attempted.

g. Opioid consumption will stop being collected at the time of the patient's discharge.

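### Patients withdrawn for an adverse event are replaced although the single dose has normally been given, and nothing in the plan keeps them in the analysis as randomised

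*Combined protocol and SAP*

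**What the plan says.** The rule is in section 9.3, under the heading on withdrawal of subjects due to adverse events: "Subjects withdrawn from study participation due to an adverse event will be replaced". The same text begins by noting: "The study drug is administered only once, at the time of the nerve block before surgery". It also gives the expected frequency: "We do not anticipate any withdrawn participants from the study, with the exception of those for which the anesthetic care plan was converted to GETA". For those conversions to general anesthesia it adds that "we do not anticipate any further data collection as being representative of a scientifically meaningful" intention-to-treat comparison.

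Four other places bear on what happens to a withdrawn patient and to the replacement:

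- Section 5.1, on missing data: "We will delete observations with missing values". No intention-to-treat or other analysis set is defined anywhere.
- Section 5.2, on safety: "The six-week incidence (and 95% CI) of individual adverse events by organ system and relatedness to the study will be calculated for each group". It proposes product-limit estimation with time running from randomization.
- Appendix 1, footnote c: if a patient withdraws after surgery "or is withdrawn by the study team during or after their surgery, they will be asked to complete Follow-Up Visit 2". No other assessment is requested after withdrawal.
- Section 4.2, on assignment: once the stratum is known, "the IDS Pharmacist will provide the next available treatment assignment envelope". Each block of five holds four MMPNA assignments and one control. No separate route is given for replacements.

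**The concern.** Replacement is usually meant to protect the number of evaluable patients when treatment is stopped early. Here there is no continuing treatment to stop. Once the block is in, withdrawal for an adverse event is a decision about observation, made because of something that happened after treatment. If the withdrawn patient then drops out of the comparison and a newcomer supplies the data, membership of the analysed group depends partly on a post-treatment outcome. Randomization does not protect against that.

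Two results are exposed. One is the primary comparison, SF-MPQ at 24 hr, which needs a score from each randomised patient. The other is the six-week adverse-event incidence by arm, which needs each dosed patient in the denominator and follow-up beyond the first event. The control arm has only 20 patients per procedure, so a few such exclusions weigh more there.

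The route is a real one. Apart from the investigators' own decisions, section 9.3 gives the independent research monitor authority to remove individual subjects.

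**Working it through.** **1. When the withdrawal falls.** The envelope is opened and the syringe prepared before the block, and the block precedes the spinal anesthetic and surgery. A withdrawal between allocation and block is possible, since adverse events are recorded from the baseline visit, but it would be the exception. Normally the dose has been given.

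**2. What the plan yields for each case.**

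- Withdrawn after the block and before 24 hr: footnote c seeks only Follow-Up Visit 2, so there is no 24-hr SF-MPQ. Section 5.1 deletes the missing observation. The replacement supplies a 24-hr score instead.
- Withdrawn after 24 hr: the 24-hr score exists. Whether it stays in the analysis once the patient has been replaced is not stated.
- Section 5.2 incidence: the event that led to withdrawal came before the withdrawal, so a product-limit estimate would count it if the patient stays in the dataset, which is also not stated. Later events in that patient would be seen only if picked up at Follow-Up Visit 2 or while a drug-associated event is being followed under section 9.2. Censoring at an adverse-event withdrawal is unlikely to be independent of later events.

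**3. Assignment of the replacement.** The documents give four MMPNA and one control per block, 80 and 20 per procedure, and 44 blocks. The allocation reproduces: 4/5 × 100 = 80 and 1/5 × 100 = 20. The envelopes number 44 × 5 = 220, which is 20 more than the 200 patients.

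Assume that a replacement takes the next envelope in its stratum, as any new enrollee does.

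- Given a withdrawn control, a replacement at an arbitrary later position is a control with probability 1/5 = 20% and MMPNA with probability 80%. If it takes the very next slot after that control, it is a control only when the first control was last in its block and the next block opens with one: 1/5 × 1/5 = 4%, so MMPNA 96%.
- Over all replacements, with equal withdrawal rates in both arms: control to MMPNA 0.2 × 0.8 = 16%; MMPNA to control 0.8 × 0.2 = 16%; MMPNA to MMPNA 0.8 × 0.8 = 64%; control to control 0.2 × 0.2 = 4%. The two cross-arm flows cancel.

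With control and MMPNA withdrawal rates c and m, and enrolment continuing to 100 completers per procedure, the expected number of controls is 100 × 0.2(1−c) / [0.2(1−c) + 0.8(1−m)]. The rates below are assumptions, since the documents give none.

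| c | m | Control : MMPNA |
|---|---|---|
| 10% | 10% | 20.0 : 80.0 |
| 10% | 0% | 18.4 : 81.6 |
| 20% | 0% | 16.7 : 83.3 |
| 20% | 5% | 17.4 : 82.6 |
| 5% | 10% | 20.9 : 79.1 |

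**4. What replacement buys in power.** Section 5.6 plans on block duration: 15 versus 30 hr, SD 7.5 and 15 hr, two-sided α = 0.05. It states 95% power at 20 versus 80 and just over 80% at 14 versus 56. Taking the larger SD (15) in both arms, the noncentrality is 15 / [15 √(1/n₁ + 1/n₂)]. At 20 versus 80 this is 1/√0.0625 = 4.00 on 98 degrees of freedom, giving 97.7%. At 14 versus 56 the power is 91.0%. The stated figures do not reproduce. They are lower than every variant tried at α = 0.05, hence conservative, and the mismatch does not affect this point.

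On the same basis:

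- two controls lost and not replaced, 18 versus 80: 96.7%; both replaced by MMPNA patients, 18 versus 82: 96.7%;
- four lost and not replaced, 16 versus 80: 95.1%; all replaced by MMPNA patients, 16 versus 84: 95.3%.

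These powers refer to block duration. Section 5.6 says there are no preliminary SF-MPQ data, so the power for the primary outcome itself cannot be computed from the documents.

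**The case against.** The strongest reply is that the sentence does less than it seems to. Section 9.2 records all observed or volunteered adverse events and follows drug-associated ones until they resolve or stabilise. Product-limit estimation from randomization would count the event behind a withdrawal. Footnote c keeps a late visit. Section 9.3 expects no withdrawals apart from conversions to general anesthesia. A patient withdrawn after 24 hr already has the primary outcome, and a mixed model could still use a withdrawn patient's other time points. Much of this stands, and it limits the size of the problem. It does not supply a 24-hr score for a patient withdrawn before then, and it does not say that withdrawn patients remain in any analysis.

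Four stronger readings are tempting and are not supported:

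- A reader might infer that event patients are exchanged for event-free ones and that reported incidence is too low by a calculable amount. The documents do not say that recorded events are discarded, and a replacement is not event-free by rule, only not withdrawn for an event.
- A reader might put a figure on the shift in mean pain by assuming how many high scorers leave. That calculation measures exclusion, not replacement, and every input would be invented.
- A reader might infer that the control arm is steadily eroded. That holds only if controls are withdrawn at a higher rate. With equal rates the flows cancel, and the next-envelope route is itself an inference.
- A reader might take the 20 assignments beyond 200 as a reserve for replacements. Section 4.2 gives them no purpose. With eight strata they may simply allow for incomplete blocks.

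It is also fair that deleting the replacement sentence alone would not cure the selection. The exclusion comes from the missing analysis set and the deletion rule, so the fix must address those too.

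**Conclusion.** The point holds in a limited form. The plan states a rule that invites selection after randomization: a patient withdrawn for an adverse event before 24 hr supplies no primary pain score, and the place goes to someone not withdrawn for an event. Later events in withdrawn patients could also be missed in the section 5.2 incidence. The handling of withdrawn GETA conversions in the same section, where intention-to-treat is set aside, gives no reassurance that other withdrawn patients would be kept.

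The size of any bias is unknown and probably small, because few such withdrawals are expected and no rates are given. The arm effect is conditional: a 20% chance that a withdrawn control is replaced by a control, assuming the next envelope is used, and no expected drift from 20:80 unless withdrawal rates differ by arm. Replacement is not needed for power, since section 5.6 already allows 30% attrition in each arm (6/20 and 24/80). This is a cheap improvement worth making, not a flaw that invalidates the design.

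**What to change.** - In section 9.3, remove replacement for anyone who has received a block, or state that added patients supplement withdrawn patients and do not take their place.
- In sections 5.1 and 5.2, state that every randomised and dosed patient stays in the pain analysis and in the adverse-event denominators by assigned arm.
- In section 9.3 and footnote c of Appendix 1, state that for patients withdrawn after the block the scheduled assessments are still sought as far as the patient is willing: the 24-hr SF-MPQ and adverse events as well as Follow-Up Visit 2. Word this so that it does not limit the research monitor's authority to remove subjects.
- Limit replacement to withdrawals before the block, and say in section 4.2 how those replacements are assigned.

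The cost is protocol wording. The downside is that a few patients with partial data are not topped up, which on the section 5.6 assumptions makes almost no difference to power.

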10.0 Resources

The following VAPHS resources will be utilized: Investigational Drug Service (IDS), Clinical Trials Center (CTC) and the Surgery and Medical Service Lines. StatCore and IDS will be used for randomization and the receipt, accountability, storage, preparation and dispensing of the study drugs, respectively. The CTC will handle all regulatory and study coordinator activities. The Surgery Service Line will be enlisted for preoperative (IMPACT Clinic), anesthesiology, and orthopedic resources, and the Medicine Service Line will be used for physical therapy resources.

11.0 Collaborations

The statistical analysis for this research study will be done in collaboration by VAPHS StatCore. Physical therapy testing at VAPHS will be conducted in conjunction with University of Pittsburgh-hired physical therapists in order to provide study-specific physical therapy coverage on weekends and/or after hours on weekdays.

APPENDIX 1: Study Calendar

	Screening Visit ^a	Baseline Visit	Day of surgery		Post-Op Day 1	Post-Op Day 2	Post-Op Day 3	Post-Op Day 4	Post-Op Day 5	Follow-Up Visit 1 ^d	Follow-Up Visit 2 ^{c, e}
			Pre-Procedure	Post-Procedure							
Clinical Assessments											
Informed Consent	X										
Determine Eligibility	X										
Demographics	X										
Orthopedic & IMPACT evaluation		X									
Crude Sensation in L2-L4 & L4-S3		X			X	X	X	X	X		X
Straight Leg Raise & Range of Motion		X			X	X	X	X	X		X
Functional Independent Measure (FIM)		X			X	X	X	X	X		X
Standing Balance Test		X			X	X	X	X	X		X
Single Leg Balance Test ^g		X									X
Gait Speed		X			X	X	X	X	X		X
Repeated Chair Stand Test		X				X	X	X	X		X
Stair Climbing Time		X									X
Physical Therapy/ Therapeutic Exercises					X	X	X	X	X		
Comorbidity (CIRS)		X									
Interim Changes											X
Discharge Disposition											X
Opioid Consumption					X ^g						
Anesthesia/Study Drugs			X								
Adverse Events		X	X	X	X	X					
Concomitant Medications		X	X	X	X	X					

	Screening Visit	Baseline Visit	Day of surgery		Post-Op Day 1	Post-Op Day 2	Post-Op Day 3	Post-Op Day 4	Post-Op Day 5	Follow-Up Visit 1	Follow-Up Visit 2 ^{c, e}
			Pre-Procedure	Post-procedure							
Questionnaires											
SFMPQ-2 ^b		X	X	X	X	X	X	X	X		X
DVPRS		X	X	X						X	X
DVPRS- in hospital ^b					X	X	X	X	X		
ORSDS ^b		X			X	X	X	X	X		
QOR-15 ^b		X			X	X	X	X	X		X
WOMAC		X									X
SF-8 ^b			X		X	X	X	X	X	X	
SF-36		X									X
Falls Questionnaire		X			X	X	X	X	X		X

a. The screening visit and baseline visit can be completed on the same day.

b. On post-op hospital days and post-op week 6 follow-up visits, these questionnaires will be completed before the subject has their first physical therapy session for the day.

c. If a patient decides to withdraw from the study after having their surgery, or is withdrawn by the study team during or after their surgery, they will be asked to complete Follow-Up Visit 2.

d. Follow-up visit 1 will occur with the patient's already scheduled standard of care follow-up orthopedic visits. Follow-Up Visit 1 may be performed as a phone call if necessary.

e. Follow up visit 2 will be scheduled to coincide with the patient's standard of care follow-up orthopedic visits.

f. Patient must pass the standing balance test first, before the single leg balance test can be attempted.

g. Opioid consumption will stop being collected at the time of the patient's discharge.

